2.4 Visit Structure

The visit structure and scheduled assessments are detailed Section 10, and Table 1.1 of the protocol. A diagrammatic explanation of the swab and treatment times can be found in Figure 6.1 of the protocol and is included below.

3 SAMPLE SIZE

Individual CFU data is presented in the study of Verhoeven 2012¹ in the absence of treatment. As the primary population for the efficacy analysis is the microbiological Intent-to-Treat (micro-ITT) set, those values with zero CFU have been excluded and the resulting data have been converted to the log¹0 CFU scale. The standard deviation (SD) of these values has been used as the estimate of variability for an analysis of change from baseline whilst including baseline log¹0 CFU as a covariate. As a result, a trial including 80 evaluable patients (40 per arm) would have a greater than 90% power to detect a true treatment effect of a 2 log¹0 CFU and an 90% power to detect a true treatment effect of a 1.5 log¹0 CFU difference between XF-73 and placebo, assuming 2-sided alpha=0.05 and a between patient SD of 2 log¹0 CFUs taken from the Verhoeven study.

It is estimated that approximately 125 patients will need to be recruited in order to have 80 patients with a burden *S. aureus* nasal carriage which will allow for the detection of a microbiological effect of XF-73 nasal gel.

4 RANDOMISATION

Patients will be randomly allocated in a 1:1 ratio as follows: 0.2% w/w XF-73 nasal gel treatment OR placebo to match XF-73 nasal gel treatment prior to dosing.

A randomization scheme will be prepared where patients will be stratified by site.

Treatment packs will be prepared according to the random code, numbered for sequential allocation to eligible study patients.

5 IDMC SAFETY REVIEW

An interim analysis will be performed, depending on recruitment projections, when approximately 60% of evaluable patients have been recruited. The interim analysis will:

- Review the Safety data generated to date.
- Review the incidence of post-operative staphylococcal infections.
- Stop the study in case of serious concerns on patient's safety.
- Stop the study due to the incidence of post-operative staphylococcal infections.

All study staff including the Sponsor will remain blinded until the end of the study.

Full details of the objectives, timing, analyses and the role of the Independent Data Monitoring Committee (IDMC) will be provided in the IDMC charter and IDMC SAP.

The IDMC safety review has been completed. The meeting took place on 5th August 2020 and it was agreed that the study should continue without modification.

6 FOLLOW-UP REVIEW

The main analysis of primary and secondary endpoints will be performed once the last patient has completed their Day 6 visit. Following this, there will be a review of relevant, longer term data, as part of the secondary and exploratory objectives, once the last patient has reached their 30 or 90-day follow-up visit depending on whether the patient had a foreign implant inserted or not. TFLs to be included in the follow-up analysis will be indicated in the TFL Shells document and will include the following data:

- Concomitant Medications
- Adverse Events
- Staphylococcal infections
- Use of post-operative staphylococcal antibiotics

7 ANALYSIS PLAN

7.1 General

Summary statistics for continuous variables will consist of number of non-missing observations (n), mean, standard deviation (SD), minimum, median, maximum, 25th and 75th percentiles unless specified otherwise. The precision of these variables is defined in the table, figure and listing shells document.

For categorical variables the number and percentage of patients in each category will be presented, based on the number of non-missing observations apart from disposition of patients, protocol deviations, background and demographic characteristics, prior and concomitant medications/procedures and adverse events where the percentage will be based on the number of patients in the analysis set.

All statistical tests will be performed using a two-tailed 5% overall significance level, unless otherwise stated. The null hypothesis at all times will be that the 0.2% w/w XF-73 nasal gel and the placebo are equivalent. All comparisons between the treatments will be reported with 95% confidence intervals for the difference.

7.2 Blinded Data Review Meeting

The Sponsor may convene a blinded data review meeting (BDRM) after the data has been cleaned and before the study is unblinded. This will be performed using blinded data taken directly from the database (i.e. TLF outputs will not be created).

The BDRM will make decisions that will include but will not be limited to assessment of protocol deviations, population assignment and if changes are required to the SAP. If required, after the BDRM and prior to database lock, a new version of the SAP will be issued.

7.3 General Derivations

This section provides details of general derivations. Derivations specific to the parameter of interest are detailed within the specific SAP section.

Definition of study day

Throughout this SAP any references to "Day XX" refer to the pre-specified visits defined in the protocol (where Day 0 is the calendar day in which surgery takes place).

Data listings will additionally present study day. Study day will be calculated relative to the first date of administration of study drug (Study Day -1).

Definition of baseline

Baseline is defined as the last non-missing value (including scheduled and unscheduled assessments) prior to the patient receiving study drug.

Incomplete dates

For calculation purposes, incomplete dates will be completed using worst case. Further details are detailed in the relevant sections as required.

Non-numeric values recorded in numeric field

In the case where a variable is recorded as ">x", " \geq x", " \leq x" or " \leq x" rather than an exact number, then for analysis purposes a value of x will be taken. Where a range of values is quoted the midpoint of the range will be taken.

Methods for handling withdrawals and missing data

In general, data will not be imputed. Where imputation may be deemed appropriate, information is detailed in the analysis descriptions.

7.4 Analysis Sets

The **Enrolled Set (ENR)** includes all patients who completed main study informed consent.

The **Safety Analysis Set** (SAF) consists of all patients who received at least one dose of study drug. Patients will be presented in the actual treatment group that they received. The primary population for the safety analyses will be the SAF set.

The **Intent-To-Treat** (ITT) set consists of all patients who were randomized. Patients will be presented in the treatment group they were randomly assigned to.

The **microbiological Intent-to-Treat** (micro ITT) set includes all patients who were randomized, received at least one dose of study drug, have at least one post-baseline assessment of S. aureus log10 CFU/mL and have a log CFU/mL result at baseline greater than 0. The primary population for the efficacy analyses will be the micro ITT. Patients will be presented in the treatment group that they were randomly assigned to.

The **Per-Protocol Set** (PPS) will be a subset of the micro ITT set consisting of those patients who do not have major protocol deviations considered to have a serious impact on the efficacy results. Patients will be presented in the actual treatment group that they received. Supportive efficacy analyses will also be performed on the PPS for key endpoints and at key time points.

All protocol deviations will be assessed and documented on a case-by-case basis by Destiny Pharma at the following intervals: monthly, prior to interim analysis, prior to database lock at Day 6 and prior to final data base lock. The protocol deviations will be classified as major or minor deviations. All major deviations will be reviewed prior to database lock, whilst blinded, to identify those considered to have a serious impact on the efficacy results, leading to exclusion from the PPS. Some categories of major protocol deviations that might be considered as having a serious impact on the efficacy results include but are not limited to:

- Patients failing specific eligibility criteria.
- Any patients with treatment administration errors.
- Taking inadmissible concomitant medication.
- Significant non-compliance with timing of study visits.
- Non-compliance of study drug administration. Patients will be considered compliant
 if they receive 5 scheduled applications (4 prior to surgery and 1 after surgery) of
 randomized study drug during the appropriate dosing windows.

This is a non-exhaustive list and additional protocol deviations other than those specified above may be identified. Protocol deviations leading to exclusion from the PPS, will be referred to as 'important' protocol deviations in the statistical outputs and

will be finalized at the population assignment meeting ahead of database lock and unblind.

The definitions for the SAF, ITT, and micro ITT analysis sets are sufficient to determine the patients included within these analysis sets and so do not require listing and agreeing prior to breaking the blind. The list of subjects included in the PPS will be agreed as far as possible prior to database lock and unblinding.

Actual study drug received will be determined using a kit list report obtained from and provided to once the blind has been broken. The report will be reconciled with the site records to confirm the correct kit was administered to each patient.

7.5 Data presentations

The data will be summarized in tabular form by treatment group apart from disposition of patients, protocol deviations and background and demographic data which will be summarized by treatment group and overall patients. Patients will not be presented for each site/country separately in the summaries unless otherwise specified. Similarly, patients will not be presented for each country separately in the listings.

Treatment group labels will be "0.2% w/w XF-73 Nasal Gel" and "Placebo XF-73 Nasal Gel" and presented in this order.

Visits and time points will be presented throughout as follows:

Case Report Form (CRF) Visit Name	Time point	SAP and TLF Terminology
Randomisation	-	Randomization
(Day -14 to Day -1)		
Treatment Period	First dose nasal swab	Baseline
(Day -1 to Day 0)	Third dose nasal swab	Prior to third dose
	Fourth dose nasal swab	Immediately prior to surgery
	Fifth dose nasal swab	Within 1 hour of incision closure
48h post wound closure	-	48 hours after surgery
Follow up (Day 6)	-	6 days after surgery
Follow up (Day 30)	-	30 days after surgery
Follow up (Day 90)	-	90 days after surgery

Only scheduled post-baseline assessments will be tabulated, post-baseline repeat/unscheduled assessments will not be tabulated although they will be listed and in particular all clinically significant values will be noted.

Eligibility, consent, completion/withdrawal and analysis set listings will be based on the enrolled set, safety listings will be based on the SAF set, and all other listings will be based on the ITT set.

Listings will be sorted by treatment, patient number and date/time of assessment.

Graphical presentations of the data will also be provided where appropriate.

Analysis sets will be summarized using the enrolled set. Study completion/withdrawal will be summarized using the ITT set. Background and demographic characteristics will be summarized using the ITT set. The primary efficacy endpoint will be summarized using the micro ITT set and the PPS. Selected secondary endpoints may be summarized using the micro ITT set and the PPS but generally will be based on the micro ITT set only. Prior and concomitant medications, administration of study drug and exposure and safety will be summarized using the SAF set.

7.6 Disposition of patients

The number and percentage of all patients enrolled, included in the SAF set, ITT set, micro ITT set and PPS, who completed the study and prematurely discontinued the study and study duration will be summarized. The number and percentage of patients will be summarized by their reasons for withdrawal from the study. In addition, the table will include the number of patients screened and the number who failed at least one inclusion or exclusion criteria. These patients will be summarized by the inclusion criteria failed. Note that patients failing screening due to a negative polymerase chain reaction (PCR) result for MSSA/MRSA carriage are not entered into the database. Therefore, a separate list of these subjects will be obtained from the interactive randomization technology system () and will be included in an appendix to the CSR.

For patients with a positive PCR result, eligibility for each of the analysis sets along with reasons for exclusion will be listed. Study completion/withdrawal data will be listed. Eligibility for the study, together with the details of any failed criteria will also be listed.

Study duration will be derived as (date of study completion or the date of early study withdrawal - date of first administration of study drug) +1.

7.7 Protocol Deviations

Destiny Pharma will review the individual deviations at the following intervals: monthly, prior to interim analysis, prior to database lock at Day 6 and prior to final data base lock. The review of protocol deviations will be performed whilst blinded to randomized treatment. See Section 7.4 for further details.

The number and percentage of patients with at least one important protocol deviation will be summarized. The number of patients with each important protocol deviation will be summarized for each important deviation category. Important protocol deviations are major protocol deviations considered to impact the evaluation of efficacy and lead to exclusion from the PPS.

Details of all important protocol deviations will be listed.

7.8 Background and Demographic Characteristics

7.8.1 Demography

Demographic characteristics (age, sex, ethnic origin and race) and body measurements (height, weight and body mass index (BMI)) collected at screening (Randomization Day -14 to Day -1) will be summarized. The number of patients within each country and within each site will also be summarized.

BMI is calculated as (weight (kg)/height (m)²).

All patient demographic data including the country where the site is based will be listed. Country will be determined from the site list relevant at the time of data extraction. Informed consent data will be listed.

7.8.2 Medical History

Medical history events will be coded using the Medical Dictionary for Regulatory Activities (MedDRA) dictionary version 23.1. This was updated to address the introduction of COVID-19 specific terms. The version used will be indicated in the data summaries and listings. The number and percentage of patients will be presented for ongoing conditions and previous conditions separately by system organ class (SOC), and preferred term (PT), where SOC and PT will be presented in decreasing frequency of the total number of patients with medical history events. Ear, nose and throat (ENT), Peri-operative and Other events will be presented in separate tables. All events will be listed.

7.8.3 Surgery

Summaries will be provided of the number of patients receiving surgery and whether this surgery involved a foreign implant. The number of patients receiving any perioperative prophylaxis interventions and the type of intervention will also be summarized. This summary will be further broken down by the time at which perioperative prophylaxis interventions were recorded – randomization, treatment period (Day -1 to Day 0) and 48 hours after surgery.

Measurements for blood glucose and body temperature will be taken between hospital admission and Dose 5. They will be entered in to the CRF under two separate collection periods (hospital admission to Dose 4 and Dose 1 to Dose 5). The collection period of interest for the listings and summaries will be Dose 1 to Dose 5.

For each patient, the percentage of blood glucose measurements over 200 mg/dL will be calculated as:

$$\frac{number\ of\ measurements\ over\ 200\ mg/dL}{number\ of\ measurements\ taken\ between\ Dose\ 1\ and\ Dose\ 5}$$

A similar calculation will be performed for the number of body temperature measurements under 35.5°c for each patient. The percentage of blood glucose measurements over 200 mg/dL and the percentage of body temperature measurements under 35.5°c will be summarized for each treatment group.

Data relating to the planned surgery (date, time and procedure), performed surgical procedure (date and time of incision, date and time of wound closure, whether the procedure involved a foreign implant), blood glucose and body temperature measurements (number of measurements taken between admission and Dose 4 and between dose 1 and dose 5 and the number of measurements over 200 mg/dL or under 35.5°c as applicable in the two periods) and the peri-operative prophylaxis interventions carried out will be listed.

7.9 Prior, Concomitant and Follow-up Period Medications

Medications will be coded using the World Health Organization Drug dictionary (WHO Drug) version 23.1. The version used will be indicated in the data summaries and listings.

Prior medications are defined as those that started and ended prior to the first administration of study drug. Medications that are either ongoing at the first administration of study drug, or started after time of first administration and on or before a patients' Day 6 visit will be deemed to be concomitant medications. If medication dates are incomplete and it is not clear whether the medication was concomitant, it will be assumed to be concomitant. Follow-up period medications are defined as those that started after a patient's Day 6 visit.

The number and percentage of patients taking concomitant medications will be summarized by medication class and standardized medication name, where medication class and standardized medication name will be presented in decreasing frequency of the total number of patients with medications. In summary tables, patients taking multiple medications in the same medication class or having the same standardized medication recorded multiple times in the study will be counted only once for that specific medication class and standardized medication name. Additional concomitant medications tables will also be summarized for patients with Peri-Prophylaxis Interventions patients with Post-operative and for Staphylococcal Antibiotics. These will be identified using the classification recorded in the CRF (those with 'Indication category' = Peri-operative prophylaxis or 'Indication category' = Post-operative anti-staphylococcal antibiotic). A medical review will be performed on an ongoing basis to ensure that indication categories are assigned correctly in the CRF.

Medication data will be listed, where medications will be flagged as prior, concomitant or follow-up period medications.

7.10 Administration of Study Drug and Exposure

Treatment exposure will be summarized by treatment group and will include the total number of patients and percentage of patients with each number of doses applied. Compliance will also be included in the summary table where a compliant subject is defined as having received all 5 doses of study drug all within the acceptable dosing windows.

Acceptable dosing windows for each dose are as follows:

- First dose: 22 hours ±2 hours before estimated incision time.
- Second dose: 14 hours ±2 hours before estimated incision time.
- Third dose: 6 hours ±2 hours before estimated incision time.
- Fourth dose: Within 1 hour before incision time.
- Fifth dose: Within 1 hour of incision closure time.

Details of the doses applied including the total number of doses applied will be listed.

7.11 EFFICACY EVALUATION

One average *S. aureus* CFU/mL value will be supplied for each patient at each swab collection time point. These data will be supplied on the original scale and will be log-transformed for analysis as appropriate. In the event that a *S. aureus* CFU/mL value is 0 (or no *S. aureus* has been detected), the value will be replaced with the next lowest meaningful value (1 CFU/mL) to enable the log transformation to be applied. Values between 0 and 1 CFU/mL are not expected.

study no: DMA18003

For all efficacy endpoints the analyses will be performed on the micro ITT set. The primary efficacy endpoint will be repeated in the PPS.

For all analyses the baseline value is defined as the swab collected prior to the first dose of study drug at approximately 24 hours prior to surgery.

The null hypothesis is that there is no difference between the treatment means for the primary endpoint. The alternative hypothesis is that there is a difference between the two treatment means (0.2% w/w XF-73 Nasal Gel - Placebo XF-73 Nasal Gel). Denoting θ_1 and θ_2 as the mean of the response variable for each treatment group respectively, the hypotheses can alternatively be expressed as:

$$H_0$$
: $\theta_1 = \theta_2$ vs. H_1 : $\theta_1 \neq \theta_2$

where H₀ is the null hypotheses and H₁ is the alternative hypothesis.

The null hypothesis of no difference in mean change between treatment groups will be assessed from the analysis of the primary endpoint. The null hypothesis will be rejected in favour of the alternative hypothesis should the probability of the test statistic, derived from observed data occurring if the null hypothesis were true (α), be less than 5% (or in other words, the two-sided p-value shows p<0.05).

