6 OVERALL DESIGN AND PLAN OF THE STUDY

6.1 Overview

This is a Phase 2, multi-centre, randomized, double-blind, parallel, placebo-controlled study of multiple applications of a single concentration of XF-73 nasal gel to assess the microbiological effect of XF-73 on commensal *S. aureus* nasal carriage in patients scheduled for surgical procedures deemed to be at high risk of post-operative *S. aureus* infection. The study is divided in 4 periods: screening (Days -14 to -1) randomization (Days -10 to -1), treatment (Days -1 and 0) and follow-up (post-last study dose to Day 30 or Day 90 if an implant is inserted during surgery). Day 0 is the calendar day in which surgery takes place. Only patients who test positive to *S. aureus* by a standardized rapid diagnostic test will be enrolled in the study. Approximately 125 patients will be randomised in a double-blind manner (the investigators and patients are blind to the treatment assignment) in a 1:1 ratio to 0.2% w/w XF-73 nasal gel treatment OR placebo to match XF-73 nasal gel.

The study drug, 0.2% w/w XF-73, or matched placebo will be administered 4 times into each nostril over 24 hours prior to surgery and then a single application immediately upon closure of surgical wound. Additionally, patients may undergo chlorhexidine skin decolonisation ahead of surgery and receive perioperative prophylactic systemic antibiotics in accordance with local practice.

In total 7 nasal swabs will be taken: at screening, 3 times prior to surgery (surgery within 1 hour), post-surgery (right after surgical wound closure), 48 hours post-surgery and 7 days post-surgery.

Efficacy will be assessed by *S. aureus* colonisation from screening to 7 days after surgery as well as by incidence of post-operative staphylococcal infections and use of anti-staphylococcal antibiotics post-surgery. Safety will be assessed by reported AEs from screening up to Day 6 as well as vital signs, physical examination (ENT), clinical laboratory assessments (haematology, clinical chemistry, and urinalysis) and Brief-Smell Identification Tests (B-SIT) at different time points as reflected in [Table 1.1](#).

The maximum study duration will be up to 45 or 105 days for each individual (from screening to post-study follow-up visit) depending on whether a foreign implant was inserted during surgery.

[figure not shown]

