9.2 Efficacy Parameters

Efficacy will be assessed by measuring CFUs/mL at the time points outlined in the Schedule of Assessments ([Table 1.1](#)) the incidence of post-operative staphylococcal infections as well as use of post-operative anti-staphylococcal antibiotics.

Any staphylococcal post-operative infections arising between study treatment and up to 30 or 90 days (if foreign implant) included but not limited to SSI, bloodstream infections, catheter-related infections, and implant infections are to be captured as events indicating lack of efficacy. These should NOT be captured as safety TEAEs.

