11.10 Determination of Sample Size

Individual CFU data is presented in the study of Verhoeven 2012²⁷ in the absence of treatment. As the primary population for the efficacy analysis is the micro-ITT, those values with zero CFU have been excluded and the resulting data have been converted to the \log_{10} CFU scale. The SD of these values has been used as the estimate of variability for an analysis of change from baseline whilst including baseline \log_{10} CFU as a covariate. As a result, a trial including 80 evaluable patients (40 per arm) would have a greater than 90% power to detect a true treatment effect of a 2 \log_{10} CFU difference and an 90% power to detect a true treatment effect of a 1.5 \log_{10} CFU difference between XF-73 and placebo, assuming 2-sided alpha=0.05, a between patient SD of 2 \log_{10} CFUs taken from the Verhoeven study.

We estimate that approximately 125 patients will need to be recruited in order to have around 80 patients with a burden *S. aureus* nasal carriage which will allow for the detection of an effect of XF-73 nasal gel.

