2.2 Study Endpoints

The primary endpoint of the study is the change in *S. aureus* log CFU/mL from baseline to pre-surgery.

The secondary endpoints are:

- Difference in AUC of S. aureus log CFU/mL from baseline to pre-surgery.
- Difference in AUC of S. aureus log CFU/mL from baseline to immediately post-surgery.
- Change in S. aureus log CFU/mL from baseline to immediately after surgery.
- Change in S. aureus log CFU/mL from baseline to 48 hours after surgery.
- Change in S. aureus log CFU/mL from baseline to 7 days after surgery.
- Percentage of patients reaching a specific reduction in S. aureus carriage prior to surgery, immediately post-surgery and on Day 6 ± 24hrs.
- Difference in the incidence of *S. aureus* post-operative infections during the 30-day period after surgery (90 days in the case of foreign implant).
- Incidence of Treatment Emergent Adverse Events (TEAEs) from the first dose of study medication to 7 days post last application of study medication.
- Changes in vital signs, safety clinical laboratory assessments, nasal examination and smell identification test.

The exploratory endpoint is the reason for post-operative prescribed anti-staphylococcal antibiotic use during the 30-day post-operative period (90 days in the case of an object implant).

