7.11.2.8 Difference in *S. aureus* Post-operative Infections

The number of patients experiencing post-operative infections will be calculated from study treatment to 30 days after surgery (or 90 days after surgery in the case of an object implant). Post-operative infections (as recorded on the 'Post-Operative

Infection' CRF page) include, but are not limited to, surgical site infection, bloodstream infections, catheter-related infections and implant infections. Descriptive statistics for the number of post-surgery days per patient will also be presented. For patients who have not reached 30 days after surgery at the time of analysis (or 90 days after surgery in the case of an object implant), the number of post-surgery days per patient will be calculated as (date of early study withdrawal – date of surgery) + 1. The number and percentage of subjects not reaching 30 days (or 90 days in the case of an object implant) will also be presented.

The number and percentage of patients with post-operative infections will be presented for each treatment group together with the severity of these infections and the bacterial strains identified.

All post-operative infection data will be listed.

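### Post-operative infections are tabulated only on the micro ITT set and kept out of the TEAEs, so a staphylococcal infection in a dosed patient outside that set reaches a listing but no table that counts infections

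*SAP*

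**What the plan says.** **Analysis set.** SAP 7.11: "For all efficacy endpoints the analyses will be performed on the micro ITT set". SAP 7.5 adds that secondary endpoints will generally use micro ITT alone, with the per-protocol set (PPS) as a second option for some. SAP 7.4 makes the PPS a subset of micro ITT. To be in micro ITT, a patient must be randomised, dosed at least once, have a post-baseline CFU result and have a baseline log CFU/mL above 0.

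**Planned size.** Protocol 6.1: "Approximately 125 patients will be randomised in a double-blind manner". Protocol 11.10 expects that "approximately 125 patients will need to be recruited in order to have around 80 patients" with a usable burden.

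**Infection endpoint.** SAP 2.2 lists it as secondary. SAP 7.11.2.8 says: "The number of patients experiencing post-operative infections will be calculated from study treatment to 30 days after surgery", or to 90 days with an implant. It plans numbers and percentages by arm, with severity and bacterial strains, and a listing of all infections. It names no analysis set. Under SAP 7.5 that listing falls on ITT.

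**Adverse events.** Protocol 9.2 treats staphylococcal post-operative infections as lack of efficacy and says of them: "These should NOT be captured as safety TEAEs". The tables in SAP 7.13.1, including those for serious events and deaths, count TEAEs. Protocol 9.3.1.2 records only drug-related SAEs after Day 6.

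**The concern.** Requiring a quantifiable baseline culture makes sense for an endpoint that is a change in CFU. It has no evident purpose for a clinical event. Patients enter on a positive PCR result; under the Schedule of Assessments no quantitative culture is done at screening, and the baseline culture swab is taken shortly before dose 1. A PCR-positive patient with a zero baseline culture can therefore be randomised, dosed, operated on and followed to Day 30 or Day 90, yet not be counted in the infection table.

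Normally the adverse event tables would pick up such an event. Here Protocol 9.2 removes that route for staphylococcal infections. The two rules together make the reported incidence of the trial's only clinical outcome incomplete. The protocol also offers monitoring of this outcome as part of its case for a placebo arm (6.2.2). With few events expected, one missing case would change the reported picture.

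**Working it through.** **1. The plan's own figure.** The 80 comes from the power statement in Protocol 11.10: 40 per arm, difference 1.5 log10 CFU, SD 2, two-sided alpha 0.05.

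- Standardised difference: 1.5 / (2 × √(2/40)) = 1.5 / 0.447 = 3.354.
- Normal approximation: Φ(3.354 − 1.960) = 0.918. Noncentral t on 78 df: 0.912.

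Both agree with the stated 90% to within 2 points, so 80 evaluable patients is a coherent planning figure.

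**2. Planned share outside micro ITT.** (125 − 80)/125 = 45/125 = 36%. If micro ITT held 70 to 90 of 125, the share would be 55/125 = 44% down to 35/125 = 28%.

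**3. Where a staphylococcal infection would be shown.**

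| Output | Set | Dosed patient inside micro ITT | Dosed patient outside micro ITT |
|---|---|---|---|
| Infection table (SAP 7.11.2.8) | micro ITT by SAP 7.11 and 7.5 | yes | no |
| TEAE, SAE and death tables (SAP 7.13.1) | SAF | no (Protocol 9.2) | no (Protocol 9.2) |
| Anti-staphylococcal antibiotic table (SAP 7.9) | SAF | the medicine, if started by Day 6 | the medicine, if started by Day 6 |
| Infection listing (SAP 7.11.2.8, 7.5) | ITT | yes | yes |

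The last column has no table that counts infections. The second row is empty for every patient, inside micro ITT or not.

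**4. How likely this is to matter.** The documents give no infection rate and say only that incidence is low (Protocol 4.3, 6.2.2). The rates p below are assumptions. With n patients outside the set, the expected number of infections is n × p and the chance of at least one is 1 − (1 − p)^n.

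| Assumed rate | Expected in 125 | Expected in 80 | Expected in 45 | Chance of at least one in 45 |
|---|---|---|---|---|
| 1% | 1.25 | 0.80 | 0.45 | 1 − 0.99^45 = 36% |
| 2% | 2.50 | 1.60 | 0.90 | 1 − 0.98^45 = 60% |
| 5% | 6.25 | 4.00 | 2.25 | 1 − 0.95^45 = 90% |

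If only 35 of the 45 were dosed and operated on, the chances become 1 − 0.99^35 = 30%, 1 − 0.98^35 = 51% and 1 − 0.95^35 = 83%.

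**5. What counts as an event.** Protocol 5.2 and SAP 2.2 define the endpoint as *S. aureus* infection. The protocol synopsis says staphylococcal. SAP 7.11.2.8 is titled *S. aureus* but counts entries on the post-operative infection CRF page, with no rule limiting them by organism. On timing, Protocol 9.2 and SAP 7.11.2.8 count from study treatment, whereas the endpoint wording in Protocol 5.2 and SAP 2.2 counts from surgery.

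**The case against.** The case on the other side has force in several places.

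- **Nothing is lost.** Every infection is in the ITT listing. This stands; the gap is in the tables, not in the data.
- **The endpoint is descriptive.** SAP 7.12 treats all secondary endpoints as descriptive, no infection test is planned, and the protocol says the trial is too small to detect an effect on infection. This stands and limits the severity.
- **No bias is shown.** A reader might infer that the restriction distorts the comparison between arms. The documents do not support that for the baseline filter: the culture is sampled before dosing. Culture-positive patients are also a defensible efficacy set for an objective about nasal carriage. What is lost is completeness.
- **Safety oversight is separate.** The IDMC reviews infection incidence under its own charter and SAP, nothing in these documents confines it to micro ITT, and SAP 5 records that its review took place on 5 August 2020. The point concerns final reporting only.
- **Antibiotics are partly covered.** SAP 7.9 already tabulates post-operative anti-staphylococcal antibiotics started by Day 6, and SAP 7.5 puts medication tables on the SAF. This stands, but such a table counts medicines rather than infections.
- **Organisms are already reported.** SAP 7.11.2.8 shows bacterial strains, so non-staphylococcal events would not be hidden. This stands; what is missing is a rule for which events make up the endpoint.
- **Other documents may name a set.** The TLF shells and IDMC SAP are separate and were not available. That is possible, but nothing in the protocol or SAP says so.

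A reader might also infer that pre-surgical infections contaminate the endpoint. That is not supported: the start of counting follows Protocol 9.2, dose 1 is planned about 22 hours before incision, and the source is the post-operative infection page. The two timing statements need only be reconciled.

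**Conclusion.** The point holds on the text of both documents. A staphylococcal infection in a dosed patient outside micro ITT would be listed but not counted as an infection in any table. A serious or fatal one, in any patient, would be in no SAE or death table. It should be fixed, but it does not threaten the primary analysis or any planned test.

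Three stronger readings go beyond the documents. First, the 36% is a planned share of patients outside the set, neither an infection rate nor an observed count. Second, not all of the 45 are shown to be dosed and operated on; some may lack a dose, surgery or a post-baseline swab, so the number at risk may be lower. Third, the gap concerns staphylococcal infections only: a non-staphylococcal infection up to Day 6 can still be a TEAE and be tabulated on the SAF.

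The chances of 36%, 60% and 90% rest on assumed rates of 1%, 2% and 5%, on 45 patients at risk, and on independence between patients.

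**What to change.** 1. In SAP 7.11.2.8, name the SAF (or ITT) as the set for the post-operative infection table, with micro ITT as supportive. The planned denominator rises from about 80 to about 125, slightly fewer on the SAF if some patients are never dosed.
2. Add a SAF table of staphylococcal infections that are serious or fatal, so that Protocol 9.2 can stand without leaving these events out of the safety tables.
3. Reconcile the endpoint wording across the protocol synopsis, Protocol 5.2, SAP 2.2 and SAP 7.11.2.8 by giving separate rows for *S. aureus*, any staphylococcal and any infection. Reconcile the start of counting between Protocol 9.2 and SAP 7.11.2.8 on one side and the endpoint wording on the other.
4. Summarise the reasons for antibiotic use in SAP 7.11.3.1 on the same set as the infections, noting that SAP 7.9 already covers antibiotics started by Day 6 on the SAF.

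The cost is SAP wording and one or two extra descriptive tables. The data are already collected, and no new patients or procedures are needed.
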